#### Patient Oriented Eczema Measure (POEM)

The POEM is a 7-item, validated questionnaire used in clinical practice and clinical trials to assess disease symptoms in children and adults with atopic eczema (Charman 2004). The format is patient response to 7 items (dryness, itching,

**flaking, cracking, sleep loss, bleeding, and weeping) based on symptom frequency during the past week and each item is a 5-point scale**

(ie., 0 = 'no days', 1 = '1 to 2 days', 2 = '3 to 4 days', 3 = '5 to 6' days, and 4 = 'every day').

The total score is the sum of the 7 items which is ranged from 0 to 28 and reflects disease-related morbidity; a high score is indicative of a poor QOL.

The following POEM banding scores have been established ([Charman 2004](#)): 0 to 2 = Clear or almost clear; 3 to 7 = Mild eczema; 8 to 16 = Moderate eczema; 17 to 24 = Severe eczema; 25 to 28 = Very severe eczema. If two or more response options are selected for a question, then the response option with the highest score is recorded. If one question of the seven is left unanswered, then that question is scored as 0 and the scores are summed and expressed as usual out of a maximum of 28. If two or more questions are left unanswered, then the questionnaire is not scored and is set to missing.

**For subjects who take rescue medication of TCS/TCI after day 29, their POEM score will be ignored on and after the date of rescue medication.**

#### Patient Global Impression of Severity (PGI-S)

The PGI-S is a single item designed to capture the subject's perception of overall symptom severity at the time of completion on a 6 point categorical response scale (0 = no symptoms, 1 = very mild, 2 = mild, 3= moderate, 4 = severe, 5 = very severe symptoms).

**For subjects who take rescue medication of TCS/TCI after day 29, their PGI-S score will be ignored on and after the date of rescue medication.**

#### Patient-reported Outcomes (PROs)

The electronic diary (eDiary), which includes the pruritus NRS, will be completed by the subject at home each morning during the treatment and follow-up periods. The remaining PROs will be conducted at the study center and should be completed prior to other study assessments to avoid the possibility of introducing bias to subject responses.

#### Pruritus Numeric Rating Scale (NRS)

**The Pruritus NRS is a simple assessment tool that patients will use to report the intensity of their pruritus (itch) during a daily recall period using electronic diary.**

Pruritus will be assessed using an NRS (0-10) with 0 = no itch and 10 = worst imaginable itch. Subjects will complete the NRS as part of the daily diary each day in the morning.

**Patients will be asked the following questions:**

**“On a scale of 0 to 10, with 0 being ‘no itch’ and 10 being the ‘worst itch imaginable’, how would you rate your itch during the previous 24 hours?”**

The mean weekly Pruritus NRS is calculated as the prorated average of the reported daily NRS within the week. For example, if there are 3 scores in a week, the prorated average = (score1 + score2 + score3)/3.

**For subjects who take rescue medication of TCS/TCI after day 29, their Pruritus NRS score will be ignored on and after the date of rescue medication.**

#### Dermatology Life Quality Index (DLQI)

The DLQI is a 10-item, subject-completed, HRQoL assessment with content specific to those with dermatology conditions. The recall period is 1 week (Finlay and Kahn, 1994). The DLQI content captures respondent perceptions of dermatology-related symptoms and feelings (embarrassment), impacts on daily activities, leisure, work or school, personal relationships, and the side effects of treatment. Each item is scored on a 4-point Likert scale: 0 = not at all/not relevant; 1 = a little; 2 = a lot; and 3 = very much (Basra et al, 2008).

#### **Handling missing items from DLQI:**

- i. If one question is left unanswered this is scored 0 and the scores are summed and expressed as usual out of a maximum of 30.**
- ii. If two or more questions are left unanswered the questionnaire is not scored.**
- iii. If question 7 is answered 'yes' this is scored 3 even if in the same question one of the other boxes is ticked.**
- iv. If question 7 is answered 'no' or 'not relevant' but then either 'a lot' or 'a little' is ticked this is then scored 2 or 1.**
- v. If two or more response options are ticked for one question, the response option with the highest score should be recorded.**
- vi. The DLQI can be analyzed by calculating the score for each of its six sub-scales.**

**When using sub-scales, if the answer to one question in a sub-scale is missing, that sub-scale should not be scored:**

Symptoms and feelings	Questions 1 and 2	Score maximum 6
Daily activities	Questions 3 and 4	Score maximum 6
Leisure	Questions 5 and 6	Score maximum 6
Work and School	Questions 7	Score maximum 3
Personal relationships	Questions 8 and 9	Score maximum 6
Treatment	Questions 10	Score maximum 3

**For subjects who take rescue medication of TCS/TCl after day 29, their DLQI score will be ignored on and after the date of rescue medication.**

Scoring of Atopic Dermatitis (SCORAD)

The SCORAD is a clinical tool with clinician and patient reported for assessing the severity (ie, extent, intensity) of AD. The tool evaluates the extent and intensity of the AD lesions, along with subjective symptoms ([Kunz et al, 1997](#)). The maximum total score is 103, with higher values indicating more severe disease.

If any component of SCORAD is missing, then SCORAD will be set to missing.

Component	Definition	Grading	Score
Extent (A)	
 
Head and neck
 
Upper limbs (anterior/posterior)
 
Lower limbs (anterior/posterior)
 
Anterior trunk
 
Back
 
Genitals
 
Hand (right/left)
 
	
 
Head and neck: 9%
 
Upper limbs: 9% each
 
Lower limbs: 18% each
 
Anterior trunk: 18%
 
Back: 18%
 
Genitals: 1%
 
Hand: 1% each
 
	Sum of each extent item score to give a total extent score A (range 0-100)
Intensity (B)	
 
Erythema (Redness)
 
Papulation/Oedema (Swelling)
 
Oozing/Crusting
 
Excoriation (Scratched)
 
Lichenification (Leathery)
 
Dryness (Ichthyosis)
 
	Each intensity item is defined on a 4-point ordinal scale: 0 = absent 1 = mild 2 = moderate 3 = severe	Sum of each intensity item score to give a total intensity score B (range 0-18)
Subjective symptoms	
 
Pruritus
 
Sleep loss
 
	Each symptom has a NRS (0-10) where 0 is no pruritus/sleep loss and 10 is the worst imaginable pruritus/sleep loss	Sum of each subjective symptom score to give a total symptom score C (0-20)
Total SCORAD score			$(A/5) + 7*(B/2) + C$

For subjects who take rescue medication of TCS/TCl after day 29, their SCORAD score will be ignored on and after the date of rescue medication.

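### The SCORAD extent items in the SAP add up to 102, which conflicts with the stated 0-100 range for extent and the stated maximum total of 103

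*SAP*

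**What the plan says.** SAP section 5.4 builds SCORAD from extent (A), intensity (B) and subjective symptoms (C), combined as A/5 + 7 × (B/2) + C.

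The extent weights, in percent, begin with "Head and neck: 9", "Upper limbs: 9% each", "Lower limbs: 18% each" and "Anterior trunk: 18". The list continues with back at 18, genitals at 1, and right and left hand at 1 apiece. The rule for A is "Sum of each extent item score to give a total extent score A (range 0-100".

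The other two components are "Sum of each intensity item score to give a total intensity score B (range 0-18" and "Sum of each subjective symptom score to give a total symptom score C (0-20".

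For the total, the SAP says: "The maximum total score is 103, with higher values indicating more severe disease". Protocol section 9.2.2.3 gives the same maximum.

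The SAP puts no cap on A. It does not say whether the upper-limb item contains the hand, and it has no rule on counting a hand once.

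**The concern.** The table is the SAP's working rule for deriving the score, and it cannot be followed in full. Adding every listed item breaks the stated range for A. Keeping to the range means that some item must be left out, reweighted or capped, and the SAP does not say which. Two programmers could reasonably derive different values from the same data.

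The score is used in several places. SCORAD at week 16 is a secondary endpoint in Part A, analysed as change from baseline with a mixed model for repeated measures (SAP 9.5.2). It is also an exploratory endpoint at weeks 24, 36 and 52 and in Part B, and it appears among the baseline disease characteristics (SAP 9.4).

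If the hand is rated within the limb and then again as its own item, a subject with hand lesions gets extra extent points. If those lesions later clear, the change from baseline includes a small amount of improvement that comes from the scoring rule.

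**Working it through.** **Inputs** (all from the SCORAD table in SAP 5.4): head and neck 9; upper limbs 9 × 2; lower limbs 18 × 2; anterior trunk 18; back 18; genitals 1; hands 1 × 2; B maximum 18; C maximum 20; total = A/5 + 7 × (B/2) + C.

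**1. The plan's own maximum.** With A = 100, B = 18 and C = 20: 100/5 + 7 × 18/2 + 20 = 20 + 63 + 20 = 103. With B and C at their maxima, the stated figure therefore requires A = 100.

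**2. The ranges of B and C.** Six intensity items scored 0-3 give 6 × 3 = 18. Two symptom scales of 0-10 give 2 × 10 = 20. Both agree with their stated ranges, so the conflict lies in the extent list.

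**3. The extent list as written.** 9 + 18 + 36 + 18 + 18 + 1 + 2 = 102, not 100.

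**4. The total as written.** 102/5 + 63 + 20 = 20.4 + 63 + 20 = 103.4, not 103.

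**5. Where the excess sits.** Without the hand items: 9 + 18 + 36 + 18 + 18 + 1 = 100. The excess of 2 equals the two hand entries.

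**6. Other readings of the list.**
- Each limb pair counted once: 9 + 9 + 18 + 18 + 18 + 1 + 2 = 75.
- Front and back of each limb weighted separately: 9 + 36 + 72 + 18 + 18 + 1 + 2 = 156.
- One hand only: 100 + 1 = 101.

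None of these gives 100.

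**7. Size for one assessment.** Two extra extent points are worth 2/5 = 0.4 SCORAD points, and one is worth 1/5 = 0.2. Relative to the scale, 0.4/103 is about 0.4%.

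**8. When the total passes 103.** Over whole-number values of A, B and C, this happens only with A = 101 (total 103.2) or A = 102 (total 103.4), and then only with B = 18 and C = 20.

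**9. Size for a treatment difference.** The documents give no data on hand involvement, so this is illustrative. Suppose the hand is counted twice, and that the arms differ only in the share of subjects whose hands go from fully involved on both sides at baseline to completely clear at week 16. The shift is then 0.4 × the difference in that share:
- 10 percentage points: 0.4 × 0.10 = 0.04
- 30 percentage points: 0.4 × 0.30 = 0.12
- 50 percentage points: 0.4 × 0.50 = 0.20

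Partial involvement or partial clearance makes the shift smaller. With hands half involved at baseline, the 30-point case gives 0.12 × 0.5 = 0.06.

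**10. Two repairs that restore the stated figures.**
- The limb entry includes the hand, and the hand items are not added: A = 100.
- The limb entry excludes the hand, and the limbs are weighted 8 each: 9 + 16 + 36 + 18 + 18 + 1 + 2 = 100.

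Either way the maximum total is 20 + 63 + 20 = 103.

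**The case against.** The strongest reply accepts the sum and disputes what follows from it. The table lists upper limbs and hands as separate items and never says that the limb weight of 9 contains the hand. If raters leave the hand out of the limb entry, nothing is counted twice, and the fault is a limb weight that is too large by 1 per side. A reader might infer that every assessment with hand lesions is over-scored. The documents do not establish this. It is the likely reading, because the other items already cover 100% and a hand is part of the arm, but the case report form and rater instructions that would settle it are not in the documents. This part of the reply stands.

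The reply also says that the effect is negligible, and this largely stands. The total exceeds 103 only with near-complete body involvement, every sign severe, and itch and sleep loss both at 10. The same rule applies in every arm. Protocol 10.3.2.2 calls the secondary analyses descriptive, and SAP 9.5 treats any secondary testing as nominal and unadjusted.

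A third argument is that the printed 0-100 range already shows the intended bound. It does, but it gives no instruction for reaching that bound, so the conflict remains. It remains even if the hands are outside the limb entry, because the listed weights add up to 102 on either reading.

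**Conclusion.** The SCORAD extent rule is wrong as written, at the lowest severity. The items add up to 102 against a stated 100, and the maximum total is 103.4 against a stated 103. This rests only on arithmetic within one table.

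Double counting of the hands is conditional on the upper-limb entry including the hand. If it does, the excess is at most 0.4 points per assessment, or 0.2 per hand.

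A reader might also infer a bias of about 0.1 point in the treatment difference. The documents do not support that as an estimate. It requires both hands to be fully involved at baseline and to clear completely, and an assumed 30-percentage-point difference between arms in that clearance. It is an upper figure for that scenario, and partial involvement or partial clearance would make it smaller.

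The primary endpoints (IGA 0/1 and EASI 75), the alpha allocation and the sample size do not use SCORAD and are unaffected.

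**What to change.** First check how the case report form and rater instructions capture the hands. Then amend the SCORAD table in SAP 5.4 so that each hand is counted once:

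- **If the upper-limb entry includes the hand:** keep the limb weight at 9% each and state that the separate hand entries are not added to A.
- **If the upper-limb entry excludes the hand:** reduce the limb weight to 8% each and keep the hand items.

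State in the table which convention applies. Do not simply delete the hand items without this check. If sites record the limb without the hand, deletion would drop real hand involvement and under-score those subjects.

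The cost is a check of the form, about one line in the SAP table and the matching line in the derivation program, settled before database lock. No new data are needed.

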**Target Treatment Effect (TTE)**

A Target Treatment Effect (TTE) for IGA 0/1 is based on an odds ratio equivalent to or greater than 5.29 comparing tezepelumab to placebo. The odds ratio of 5.29 is determined by the following assumption: tezepelumab response rate is 37% and placebo rate is 10% (Simpson et al, 2016). The observed placebo rate may be

different from the assumed 10%, therefore, the target tezepelumab response rate may be adjusted fixing the odds ratio at 5.29.

A Target Treatment Effect (TTE) for EASI 75 is based on an odds ratio equivalent to or greater than 5.67 comparing tezepelumab to placebo. The odds ratio of 5.67 is determined by the following assumption: tezepelumab response rate is 50% and placebo rate is 15% ([Simpson et al., 2016](#)). The observed placebo rate may be different from the assumed 15%, therefore, the target tezepelumab response rate may be adjusted fixing the odds ratio at 5.67.

## 5.5 Primary Endpoints

### IGA 0/1 at week 16

The primary endpoint, IGA 0/1 at week 16 in the absence of rescue medication of TCS/TCI from day 29 to week 16 in Part A, will be derived as follows:

- Derive IGA 0/1 at week 16 as 1, if the IGA score is 0 or 1 at week 16 and no rescue medication of TCS/TCI from day 29 to week 16
- IGA 0/1 at week 16 will be missing if there is no IGA assessment at week 16 and either no rescue medication of TCS/TCI from day 29 to week 16 or the use of rescue medication is unknown during day 29 to week 16
- Otherwise derive IGA 0/1 at week 16 as 0

### EASI 75 at week 16

The primary endpoint, EASI 75 at week 16 in Part A, will be derived as follows

- Derive EASI 75 at week 16 as 1, if there is greater than or equal to 75% improvement in EASI score from baseline and no rescue medication of TCS/TCI from day 29 to week 16
- EASI 75 at week 16 will be missing if there is no EASI assessment at week 16 and either no rescue medication of TCS/TCI from day 29 to week 16 or the use of rescue medication is unknown during day 29 to week 16
- Otherwise derive EASI 75 at week 16 as 0.

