7.1.5 Other Treatment Procedures

During the 28-day screening period, subjects must discontinue from all AD therapies, except for approved moisturizers (see [Section 7.1.7](#)), for at least the 7 consecutive days immediately prior to day 1. During the study, approved moisturizers are allowed to be applied, with the exception of 8 hours prior to any scheduled visit.

Medications and procedures permitted at any time during the study for subjects enrolled in Part A and Part B include:

- Basic skin care (cleansing and bathing), emollients, bleach baths, topical anesthetics, and antihistamines (all for any duration)
- Medications used to treat chronic diseases such as diabetes, hypertension, and asthma

Part A

In Part A of the study, if needed to control intolerable AD symptoms, rescue treatment for AD may be provided at the discretion of the investigator. Rescue is not allowed in the first 4 weeks of Part A. Topical calcineurin inhibitors may be used for rescue, but are to be reserved for problem areas only (eg, face, neck, intertriginous and genital areas). Investigators are to attempt to limit the first step of rescue therapy to topical medications, and escalate to systemic medications only for subjects who do not respond adequately following at least 7 days of topical treatment. If a subject receives rescue treatment with systemic corticosteroids or nonsteroidal systemic immunosuppressive drugs

(eg, cyclosporine, mycophenolate-mofetil, azathioprine), study treatment is to be immediately discontinued.

All subjects are to complete the schedule of study visits and assessments whether or not they complete study treatment or receive rescue treatment for AD.

Part A Rescue Guidance

Subjects who use TCS are to apply medium potency TCS once daily to areas with active lesions. Low potency TCS should be used once daily on areas of thin skin (eg, face, neck, intertriginous, genital areas, areas of skin atrophy) or for areas where continued treatment with medium potency TCS is considered unsafe.

Triamcinolone acetonide 0.1% cream or fluocinolone acetonide 0.025% ointment are recommended as medium potency TCS therapy; hydrocortisone 1% cream is recommended as low potency TCS therapy. After lesions are under control (clear or almost clear), subjects are to switch from medium potency to low potency TCS and treat once daily for 7 days, then cease TCS therapy.

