7.4.2 Dosage Adjustments, Delays, Rules for Withholding or Restarting, Permanent Discontinuation

7.4.2.1 Amgen Investigational Product: Tezepelumab

The reason for dose change of tezepelumab is to be recorded on each subject's CRF(s).

An individual subject may be discontinued at the discretion of the investigator and/or the sponsor due to clinically significant events.

In Part A of the study, subjects who are determined to be non-responders will receive tezepelumab 420 mg SC Q2W for the remainder of the study, beginning with the week 18 dose. Non-responders are defined as those subjects who have not achieved at least a 50% improvement in EASI at week 16 compared to baseline (day 1). The randomized treatment assignments for the non-responders will remain blinded until the end of study.

Subjects who receive rescue therapy with topical medications may continue treatment with study drug, per the instructions outlined in [Section 7.1.5](#).

If a subject receives rescue treatment with systemic corticosteroids or nonsteroidal systemic immunosuppressive drugs (eg, cyclosporine, mycophenolate-mofetil, azathioprine), study treatment is to be immediately discontinued. All subjects are to complete the schedule of study visits and assessments whether or not they complete study treatment or receive rescue treatment for AD.

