8.1 Discontinuation of Study Treatment

Subjects (or a legally acceptable representative) can decline to continue receiving investigational product and/or other protocol-required therapies or procedures at any

time during the study but continue participation in the study. If this occurs, the investigator is to discuss with the subject the appropriate processes for discontinuation from investigational product or other protocol-required therapies and must discuss with the subject the possibilities for continuation of the Schedule of Activities (see [Table 2-1](#) and [Table 2-2](#)) including different options of follow-up (eg, in person, by phone/mail, through family/friends, in correspondence/communication with other treating physicians, from the review of medical records) and collection of data, including endpoints, adverse events, disease-related events, and must document this decision in the subject's medical records. Subjects who receive systemic rescue therapies will be discontinued from study treatment but whenever safe and feasible, it is imperative that subjects remain on-study to ensure safety surveillance and/or collection of outcome data. Subjects who have discontinued investigational product and/or other protocol-required therapies or procedures should not be automatically removed from the study. Whenever safe and feasible, it is imperative that subjects remain on-study to ensure safety surveillance and/or collection of outcome data.

Subjects may be eligible for continued treatment with Amgen investigational product(s) and/or other protocol-required therapies by a separate protocol or as provided for by the local country's regulatory mechanism, based on parameters consistent with [Appendix 3](#).

Reasons for removal from protocol-required investigational product(s) or procedural assessments include any of the following:

- Decision by Sponsor
- Lost to follow-up
- Death
- Ineligibility determined
- Protocol deviation
- Non-compliance
- Adverse event
- Subject request
- Pregnancy

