## 2. Objectives, Endpoints and Hypotheses

### 2.1 Objectives and Endpoints

Objectives	Endpoints
Primary – Part A	

To evaluate the effect of tezepelumab compared with placebo, assessed using the Investigator's Global Assessment (IGA) and Eczema Area and Severity Index (EASI)

	

IGA score of 0 (clear) or 1 (almost clear) (IGA 0/1) at week 16

75% reduction in EASI (EASI 75) at week 16

The first primary estimand consists of:

- Target population – patients with moderate-to-severe atopic dermatitis (**AD**).
- Endpoint – IGA 0/1 at week 16.
- Intercurrent event – there are 2 intercurrent events, discontinuation of IP before week 16 and **concurrent use** of rescue medication **with TCS/TCI** between day **29** and week 16. Treatment effects will be estimated for subjects regardless of whether patients complete 16 weeks of **study treatment**. The use of rescue medication is captured through the endpoint definition in **Section 5.5, and use of TCS/TCI will be classed as a non-response**.
- Summary measure – odds ratio comparing the odds of achieving endpoint on tezepelumab 420 mg Q2W compared to the odds of achieving endpoint on placebo.

In summary, the first primary estimand is the odds ratio between tezepelumab 420 mg Q2W and placebo in achieving IGA 0/1 at week 16, in the absence of rescue medication with **TCS/TCI regardless of whether patients complete 16 weeks of study treatment**, in patients with moderate-to-severe AD.

The second primary estimand is the odds ratio between tezepelumab 280 mg Q2W and placebo in achieving IGA 0/1 at week 16, in the absence of rescue medication with **TCS/TCI regardless of whether patients complete 16 weeks of study treatment**, in patients with moderate-to-severe AD.

The third primary estimand is the odds ratio between tezepelumab 420 mg Q2W and placebo in achieving EASI 75 at week 16, in the absence of rescue medication with **TCS/TCI regardless of whether patients complete 16 weeks of study treatment**, in patients with moderate-to-severe AD.

The fourth primary estimand is the odds ratio between tezepelumab 280 mg Q2W and placebo in achieving EASI 75 at week 16, in the absence of rescue medication with **TCS/TCI regardless of whether patients complete 16 weeks of study treatment**, in patients with moderate-to-severe AD.

Secondary – Part A	

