## 5.4 Study Endpoints

### Investigator's Global Assessment (IGA)

The IGA allows investigators to assess overall disease severity at 1 given time point and consists of a 6-point severity scale from clear to severe disease (0 = clear; 1 = almost clear; 2 = mild disease; 3 = moderate disease; 4 = severe disease; 5 = very severe disease). The IGA uses clinical characteristics of erythema, infiltration, papulation, oozing, and crusting as guidelines for the overall severity assessment ([Breuer et al, 2004](#)).

**For subjects who take rescue medication of TCS/TCI from day 29, their IGA score will be ignored on and after the date of rescue medication.**

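### Only TCS/TCI rescue counts as non-response in Part A, so a subject given systemic rescue for AD without TCS/TCI can be derived as a week-16 primary responder

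*SAP*

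**What the plan says.** SAP 2.1 names two intercurrent events for the primary estimands.

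- **Stopping investigational product before week 16.** The observed outcome is used: "Treatment effects will be estimated for subjects regardless of whether patients complete 16 weeks of" study treatment.
- **Rescue with TCS/TCI between day 29 and week 16.** Here "use of TCS/TCI will be classed as a non-response".

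SAP 5.5 puts this into the derivation. IGA 0/1 is 1 if "the IGA score is 0 or 1 at week 16 and no rescue medication of TCS/TCI from day 29 to week 16", and EASI 75 carries the same clause. SAP 5.4 adds that, for subjects who take TCS/TCI rescue from day 29, "their IGA score will be ignored on and after the date of rescue medication"; EASI has a matching sentence. None of these sections mentions systemic rescue.

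The protocol does. Section 7.1.5 tells investigators to try to keep the first step of rescue topical and to "escalate to systemic medications only for subjects who do not respond adequately following at least 7 days of topical treatment". If systemic corticosteroids or non-steroidal systemic immunosuppressants are given, study treatment stops (7.1.5, 7.4.2.1), but all subjects are to "complete the schedule of study visits and assessments whether or not they complete study treatment or receive rescue treatment for AD". Section 8.1 says the same: "Subjects who receive systemic rescue therapies will be discontinued from study treatment but whenever safe and feasible, it is imperative that subjects remain on-study".

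**The concern.** Part A is a monotherapy comparison, and protocol 3.1 explains that abstaining from TCS was chosen to reduce confounding. The SAP protects that comparison against topical corticosteroids and calcineurin inhibitors, but not against systemic drugs used for the same purpose. A subject who receives a systemic drug falls, by default, under the rule for stopping investigational product, so the observed week-16 score is used. A clear or almost-clear skin score reached on the systemic drug would then be credited to the randomised arm in any of the four primary estimands.

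The direction cannot be known in advance. If such rescue is commoner on placebo, the treatment effect is diluted. If it is commoner on tezepelumab, the effect is inflated.

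**Working it through.** **Step 1. Trace the rule (SAP 2.1, 5.4, 5.5, 9.5.1.1, 9.5.1.2).** Each subject is in Part A.

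| Course up to week 16 | Primary derivation |
|---|---|
| TCS/TCI from day 29; criterion met at week 16 | 0 |
| Systemic rescue after TCS/TCI from day 29; criterion met | 0 |
| Systemic rescue, no TCS/TCI from day 29; criterion met | **1** |
| Systemic rescue, no TCS/TCI from day 29; no week-16 assessment | missing, then 0 by non-responder imputation |

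The third row is the gap. Non-responder imputation does not reach it, because the endpoint is derivable. The analysis set is all randomised subjects, so nobody is excluded. The three sensitivity analyses (multiple imputation, LOCF, added IgE covariate) leave the rescue rule as it is. In the fourth row, multiple imputation or LOCF could also turn the 0 into a 1.

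**Step 2. Reproduce the plan's power (SAP 3.2).** Inputs: 60 per arm less 10% dropout gives n = 54; two-sided alpha 0.025, so z = 2.2414; rates 10% and 40% (IGA 0/1), 15% and 50% (EASI).

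Power = Φ{[Δ − z√(2p̄(1−p̄)/n)] / √([p1(1−p1)+p2(1−p2)]/n)}

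- IGA: (0.30 − 2.2414 × 0.08333)/0.07817 = 1.448, power 92.6%.
- EASI: (0.35 − 2.2414 × 0.09014)/0.08361 = 1.770, power 96.2%.

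Both meet the stated floor of at least 85%.

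**Step 3. Illustrate the size.** The documents give no rate of systemic-only rescue. Assume 1-2% of an arm, half of whom reach response, which adds 0.5-1.0 percentage points to that arm's response rate. Keep 60 per arm and count the 10% dropouts as non-responders: IGA 9% versus 36%, EASI 75 13.5% versus 45%. Power is by exact enumeration of all 61 × 61 outcomes at alpha 0.025, without the planned baseline covariate.

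| Scenario | Rates | Chi-square / Wald power | Odds ratio |
|---|---|---|---|
| IGA, none | 9 vs 36% | 92.9 / 91.5% | 5.69 |
| IGA, placebo only, 1% | 9.5 vs 36% | 91.5 / 90.1% | 5.36 |
| IGA, placebo only, 2% | 10 vs 36% | 90.0 / 88.5% | 5.06 |
| IGA, both arms, 1% | 9.5 vs 36.5% | 92.4 / 91.1% | 5.48 |
| IGA, both arms, 2% | 10 vs 37% | 91.9 / 90.7% | 5.29 |
| IGA, tezepelumab only, 1-2% | 9 vs 36.5-37% | higher than base | 5.81-5.94 |
| EASI 75, none | 13.5 vs 45% | 95.6 / 95.2% | 5.24 |
| EASI 75, placebo only, 1-2% | 14-14.5 vs 45% | 94.8-93.9 / 94.3-93.4% | 5.03-4.82 |

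Chance of at least one such responder in an arm of 60: 1 − 0.995^60 = 26% to 1 − 0.99^60 = 45%.

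**Step 4. How far it would have to go.** With the step 2 formula (n = 54) and the extra responders all on placebo, one takes IGA power from 92.6% to 87.6% and two take it to 81.1%. Two of 54 is 3.7% of the arm, or about 7.4% with systemic-only rescue if half respond.

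**Step 5. One subject at the boundary.** Responders of 60, placebo versus tezepelumab, at the initial 0.025 level (chi-square, Wald, likelihood-ratio p):

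- 5 vs 15: 0.014, 0.019, 0.013 (passes).
- 6 vs 15: 0.031, 0.036, 0.028 (fails; it would pass at a 0.05 retest).
- 6 vs 16: 0.018, 0.023, 0.017 (passes).

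At true rates of 9% and 36%, adding one placebo responder reverses significance in about 4.6% (chi-square) to 4.8% (Wald) of trials, before allowing for the chance that such a subject exists.

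**The case against.** **The path is narrow.** This stands. Rescue is barred in the first 4 weeks of Part A, topical treatment comes first, and a subject who uses TCS/TCI from day 29 is already a non-responder. Protocol 7.1.7 also lists systemic immunosuppressive drugs as prohibited. But 7.1.5 asks investigators only to attempt the topical step, and criterion 108 admits some subjects for whom topical treatment is inadvisable. The exception can occur. Its rarity lowers the severity and leaves the derivation as it is.

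**It may be a deliberate treatment-policy choice.** Systemic rescue means stopping investigational product, and SAP 2.1 says what happens then, so the endpoint is defined. That is fair, but systemic rescue is never mentioned, so intent cannot be read from the text. If it is intended, the SAP should say so.

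**Stronger readings that a reader might infer are not supported:**

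- *That any topical rescue makes a subject a non-responder.* The contrast holds only for TCS/TCI from day 29 to week 16. Earlier use, or a topical that is neither, does not trigger the rule.
- *That the SAP contradicts itself because 9.5.2 censors time to EASI response at rescue medication.* The term is undefined there and may mean TCS/TCI, since SAP 2.1 describes the secondary estimands like the primary ones. It is an ambiguity.
- *That such cases would be invisible.* SAP 9.6.9 names only TCS and TCI, but deviation tables (8.4) and reasons for stopping investigational product (9.2) may show some. Under "Reasons for removal from protocol-required investigational product(s) or procedural assessments include any of the following" protocol 8.1 gives nine reasons, none of them rescue, so this view is partial. Some SAP sections and the Supplemental SAP were not available.

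**Conclusion.** The point holds as a minor gap in the derivation. As written, a Part A subject given systemic rescue for AD, with no TCS/TCI from day 29 to week 16 and an observed score meeting the criterion, is a primary responder; the same score after TCS/TCI in that window is not.

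The size rests on assumptions. With 1-2% systemic-only rescue and 50% response among those subjects, neither of which is in the documents, an arm's rate moves by at most 1 point and power stays above 85%. The 50% is generous, since the plan expects 40% IGA response in its highest dose group. A reader might infer that the trial is underpowered or biased against tezepelumab. The documents support neither: they give no rescue rate and no split by arm, and power would fall below 85% only with a much larger, one-sided imbalance. One subject could change a conclusion only in a result close to the boundary.

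**What to change.** Before unblinding, for Part A:

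1. In SAP 2.1 and 5.5, add an intercurrent event: a systemic corticosteroid, non-steroidal systemic immunosuppressant, or other prohibited systemic or biologic treatment, given for AD by its recorded indication, up to the week-16 assessment. State the start day of the window. The indication matters because asthma medication is permitted, and a steroid course for asthma should not be scored as AD failure.
2. Derive it directly as 0. If the score were only ignored under 5.4, the endpoint could become missing under 5.5, and multiple imputation or LOCF could restore a response.
3. Align SAP 5.4, the EASI 50/90 endpoints and the later Part A time points, and define rescue medication in 9.5.2 to match.
4. Add one sensitivity analysis using observed scores after systemic rescue, and add systemic rescue by arm to 9.6.9.

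The cost is SAP wording, one derivation line, one analysis and one table row. Protocol 7.8.2 already collects concomitant therapies from first dose with indication and start and stop dates. The downside is a slightly lower responder count. Sample size, alpha and patient care do not change.

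Two separate points remain for the sponsor: protocol 7.1.5 and 7.1.7 must be reconciled on systemic drugs in Part A, and the SAP 5.6 TCS/TCI rule needs clarifying for Part B, where background TCS is allowed.
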